1.2.2.2 Crohn's Disease

RPC01-2201, a Phase 2 study was conducted in CD, to examine endoscopic and clinical outcomes following treatment with ozanimod 0.92 mg daily for 12 weeks. Simple Endoscopic Score for Crohn's Disease (SES-CD) reductions of $\geq 50\%$ from baseline were seen in 28.6% of subjects (observed cases) as measured by paired segments, with greater endoscopic response in subjects with baseline SES-CD score ≤ 12 and a shorter disease duration. At week 52, the proportion of subjects achieving reductions of $\geq 50\%$ was maintained at 26.7%. Clinical response was seen in 68.5% and 93.8% of subjects (observed cases) at Week 12 and Week 52, respectively. Clinical remission was seen in 46.3% and 65.6% of subjects (observed cases) at Week 52, respectively.

[figure not shown]
The safety and tolerability results from the 12-week Induction Period of RPC01-2201 suggest that ozanimod 0.92 mg daily is well tolerated and has an acceptable safety profile in subjects with moderately to severely active CD. In the open-label period (OLP), ozanimod 0.92 mg was well tolerated and there were no new safety concerns. The AEs reported in the study were generally consistent with those seen in subjects with moderately to severely active UC.

Please refer to the Investigator's Brochure for detailed information concerning the available pharmacology, toxicology, drug metabolism, clinical studies, and AE profile of the IP.

1.2.3 Rationale for Dose Selection

Results from single ascending dose and multiple ascending dose studies in Phase 1 were utilized to select appropriate doses for Phase 2 studies. The Phase 2 trial of ozanimod in UC was conducted comparing 0.92 mg and 0.46 mg of ozanimod with placebo. Safety was comparable across both ozanimod arms, and the 0.92 mg/day dose arm demonstrated better efficacy as compared to the 0.46 mg/day dose arm across various clinical and endoscopic endpoints ([Sandborn, 2016](#)). Results suggested a dose dependent efficacy response, making 0.92 mg more favorable for future investigation.

The favorable clinical results and the available safety data from the Phase 2 and Phase 3 UC studies as described above, as well as supportive clinical and safety data from the completed Relapsing Multiple Sclerosis (RMS) program provide additional data to support the use of the 0.92 mg dose of ozanimod. Data from 52 weeks of treatment (RPC01-2201) in subjects with active CD treated with ozanimod 0.92 mg suggest clinical benefit based on clinical, endoscopic, histologic and  responses with a comparable safety profile to subjects previously evaluated with ozanimod. The overall data supported evaluating the 0.92 mg dose in the ozanimod CD program.

Please refer to the Investigator's Brochure for detailed information concerning the available pharmacology, toxicology, drug metabolism, clinical studies, and AE profile of the IP.

1.3 Study Rationale

Given the mechanism of action of ozanimod, data from the preclinical animal model, the positive results from the Phase 2 UC study, RPC01-202, and preliminary results from the Induction Period

of the Phase 2 study in CD, RPC01-2201, a Phase 3 program with ozanimod in CD is being conducted.

The current study is designed to assess the long-term safety and explore long-term efficacy of ozanimod in subjects with moderately to severely active CD. This study will allow subjects who are receiving clinical benefit from ozanimod the opportunity to continue to receive IP and experience potential long-term endoscopic benefit. For subjects who are not in clinical response and/or clinical remission after completing 12 weeks in the Induction Studies, this study provides an opportunity for potential delayed clinical benefit.

1.4 Benefit/Risk Assessment

The assessment of potential risks for identified safety findings, as well as the risk mitigations, are summarized in the table below. More detailed information about the known and expected benefits and risks and reasonably anticipated adverse events (AEs) of ozanimod may be found in the IB.

Individual benefit/risk considerations remain the responsibility of the investigator. Investigators should apply clinical judgment, and these risks should be considered when managing a patient and when deciding if continuation of treatment with ozanimod is warranted.

1.4.2 *Benefit Assessment*

The benefit of ozanimod for the treatment of UC is established. See [Section 1.2.2.1](#) for details. Preliminary results from a non-controlled Phase 2 trial in CD indicated that subjects derived clinical and endoscopic benefit from treatment with ozanimod. See [Section 1.2.2.2](#) for details.

1.4.3 *Overall Benefit Risk Conclusion*

Despite recent progress in CD treatment, there remains an unmet need for agents that are safe and convenient oral treatments and can provide effective induction and long-term maintenance of clinical remission. The benefit/risk profile for ozanimod has been evaluated for the indication of CD. Results from subjects with moderate to severe disease who previously failed prior therapy and were treated with ozanimod 0.92 mg daily for at least 12 weeks suggested clinical and endoscopic benefit. In addition, the safety results suggest that ozanimod is well tolerated in patients with CD and is consistent with that observed in other patient populations (UC and RMS). The overall data to date suggest that this ozanimod Open-Label Extension Study (RPC01-3204) has a potential favorable benefit/risk profile for patients with active CD.

2 STUDY OBJECTIVES AND ENDPOINTS

2.1 Study Objective

- Demonstrate the long-term safety and explore long-term efficacy of ozanimod for the treatment of subjects with moderate to severely active CD.

2.2 Study Endpoints

Note: Endpoints will be evaluated annually for up to 264 weeks.

2.2.1 *Efficacy Endpoints:*

- Proportion of subjects with a CDAI score of < 150
- Proportion of subjects with a SES-CD decrease from baseline of $\geq 50\%$
- Proportion of subjects with average daily abdominal pain score ≤ 1 point, and average daily stool frequency ≤ 3 points with abdominal pain and stool frequency no worse than baseline
- Proportion of subjects with CDAI reduction from baseline of ≥ 100 points or CDAI score of < 150
- Proportion of subjects with absence of ulcers ≥ 0.5 cm with no segment with any ulcerated surface $\geq 10\%$
- Proportion of subjects with CDAI reduction from baseline of ≥ 70 points
- Change from baseline in CDAI
- Proportion of subjects with CDAI reduction from baseline of ≥ 100 points or CDAI score of < 150 and SES-CD decrease from baseline of $\geq 50\%$
- Proportion of subjects with CDAI score of < 150 and SES-CD ≤ 4 points and a SES-CD decrease ≥ 2 points
- Proportion of subjects with average daily abdominal pain score ≤ 1 point and average daily stool frequency ≤ 3 points with abdominal pain and stool frequency no worse than baseline and SES-CD ≤ 4 points and a SES-CD decrease ≥ 2 points
- Proportion of subjects with SES-CD ≤ 4 points and a SES-CD decrease ≥ 2 points
- Proportion of subjects with a CDAI score < 150 in subjects off corticosteroids
- Proportion of subjects with a Crohn's Disease Endoscopic Index of Severity (CDEIS) decrease from baseline of $\geq 50\%$

2.2.3 *Overview of Safety Assessments*

The incidence, severity, relationship, and type of treatment-emergent adverse events (TEAEs), serious adverse events (SAEs), and AEs leading to discontinuation of IP will be summarized (see [Section 14](#)), as well as clinically meaningful changes from baseline for clinical laboratory measures, vital signs, and electrocardiograms (ECGs). [REDACTED]

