4.2 Inclusion Criteria

Subjects must satisfy the following criteria to be enrolled in the study:

[figure not shown]
1. Subjects who are not in clinical response and/or clinical remission after completing 12 weeks in the Induction Studies RPC01-3201 or RPC01-3202, subjects who experience relapse in the Maintenance Study RPC01-3203, subjects who complete the Maintenance Study RPC01-3203, subjects who complete at least 1 year of RPC01-2201.
2. Subject should not have any constraints under local regulations, must provide written informed consent prior to any study-related procedures, and must have the ability to comply with the [REDACTED]
3. Female subjects of childbearing potential (FCBP):

Note: For the purposes of this study, a female subject is considered to be of childbearing potential if she 1) has not undergone a hysterectomy (the surgical removal of the uterus) or bilateral oophorectomy (the surgical removal of both ovaries) or 2) has not been postmenopausal for at least 24 consecutive months (that is, has had menses at any time during the preceding 24 consecutive months).

Must agree to practice a highly effective method of contraception throughout the study until completion of the [REDACTED] Safety Follow-up Visit. Highly effective methods of contraception are those that alone or in combination result in a failure rate of a Pearl Index of less than 1% per year when used consistently and correctly. Examples of acceptable methods of birth control in the study are the following:

- combined hormonal (containing oestrogen and progestogen) contraception, which may be oral, intravaginal, or transdermal
- progestogen-only hormonal contraception associated with inhibition of ovulation, which may be oral, injectable, or implantable
- placement of an intrauterine device (IUD)
- placement of an intrauterine hormone-releasing system (IUS)
- bilateral tubal occlusion
- vasectomized partner
- complete sexual abstinence

Periodic abstinence (calendar, symptothermal, post-ovulation methods), withdrawal (coitus interruptus), spermicides only, and lactational amenorrhoea method are not acceptable methods of contraception. Female condom and male condom should not be used together.

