8.1.1 Corticosteroid Taper

If subjects are still receiving corticosteroids in the Open-label Extension Study, subjects should begin tapering corticosteroids once clinical response or clinical remission has been achieved.

8.1.2 *Aminosalicylates or Purified Medicinal Probiotics*

Subjects receiving 5-aminosalicylic acid (ASA) or purified medicinal probiotics should maintain a stable dose throughout the study unless reduction or discontinuation is clinically indicated.

[figure not shown]
8.1.3 *COVID-19 Vaccination*

COVID-19 vaccines that are NOT live are allowed and should be handled in the same manner as other vaccines. Administration may occur during the study, including during treatment with IP and after the last dose of IP.

Non-live COVID-19 vaccination is considered a simple concomitant medication within the study. However, the efficacy and safety of non-live vaccines (including non-live COVID-19 vaccines) in subjects receiving ozanimod is unknown. The individual benefit/risk assessment of a vaccine remains with the Investigator. If the assessment of the Investigator suggests the vaccine to be beneficial, it must be a non-live, replication incompetent vaccine, and be approved or otherwise authorized (eg, Emergency Use Authorization [FDA] or equivalent) by national health authorities.

See [APPENDIX B](#) for further SARS-CoV-2 guidance.

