9 STATISTICAL CONSIDERATIONS

Detailed methodology for summary and statistical analyses of the data collected in this study will be documented in a Statistical Analysis Plan (SAP), which will be maintained by the sponsor. The SAP may modify the plans outlined in the protocol; however, any major modifications of the key endpoint definitions and/or its analysis will also be reflected in a protocol amendment.

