9.2 Study Population Definitions

All subjects who receive at least 1 dose of IP will comprise both the Intent-to-Treat (ITT) population and the Safety population. These populations will be used to summarize all safety and efficacy data, respectively.

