9.6 Efficacy Analysis

Due to the open-label nature of the study and the lack of a control group, all data will be summarized, and no hypothesis testing will be performed. Each efficacy endpoint will be summarized and [REDACTED] around the estimates may also be presented. All efficacy data will be listed.

For all proportion-based efficacy endpoints, subjects with missing efficacy data will be considered non-responders.

For continuous efficacy endpoints, subjects with missing data will have their last post-baseline value carried forward.

Observed-cases analyses will also be presented for all efficacy endpoints.

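### The endpoint for remission off corticosteroids takes only subjects off steroids as its denominator, so it overstates steroid-free remission and can hold steady or rise while that rate falls

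*Combined protocol and SAP*

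**What the plan says.** Section 2.2.1 and the Protocol Summary word the endpoint identically: "Proportion of subjects with a CDAI score < 150 in subjects off corticosteroids". Endpoints are evaluated annually for up to 264 weeks. Other composite endpoints in the list join their conditions with 'and', for example the one that begins "Proportion of subjects with CDAI score of < 150 and SES-CD".

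On steroid use, Section 8.1.1 says of subjects still receiving corticosteroids: "subjects should begin tapering corticosteroids once clinical response or clinical remission has been achieved".

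Two general analysis rules apply. Section 9.2 makes everyone who received at least one dose both the ITT and the Safety population, and adds: "These populations will be used to summarize all safety and efficacy data, respectively". Section 9.6 says: "For all proportion-based efficacy endpoints, subjects with missing efficacy data will be considered non-responders". It also promises observed-case analyses of every efficacy endpoint and rules out hypothesis testing.

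Section 9 leaves detail to a separate plan: "Detailed methodology for summary and statistical analyses of the data collected in this study will be documented in a Statistical Analysis Plan (SAP"). No SAP text defining this endpoint is in the documents supplied for this review. The protocol does not say whether 'off' means off at the visit, off for a minimum period, or off at entry.

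**The concern.** A reader of a five-year extension wants to know what share of treated subjects are in remission without steroids. The endpoint as worded answers another question: among those off steroids at the visit, what share are in remission?

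The difference matters because the denominator is formed after treatment starts. A subject who enters on steroids and does not respond has no trigger to taper, tends to stay on steroids, and so leaves the calculation instead of counting as a failure. Subjects off steroids at entry stay in whatever their response, which dilutes the effect but does not remove it. The denominator can also change from one annual visit to the next, so a trend across years mixes changes in remission with changes in who is counted.

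The two general rules do not settle the matter. Section 9.2 names a population but does not say how a subject still on steroids is classified. Section 9.6 covers missing efficacy data, but a subject on steroids with a recorded CDAI is not missing. Missing steroid status is not mentioned.

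**Working it through.** The plan states no expected rate, sample size or power for this endpoint, so there is no figure to reproduce.

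**1. The bound needs no assumptions.** Let N be all ITT subjects, O those off steroids at the visit, and R those off steroids with CDAI < 150. The figure as worded is R/O and the joint rate is R/N. Since O ≤ N, R/O ≥ R/N. The ratio of the two is N/O: 1.25 with 80% off steroids, 1.67 with 60%, 2.5 with 40%.

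**2. Model for the size.** Let p be the share on steroids at entry, r the response rate, m the remission rate, and t₁ and t₂ taper completion in remitters and in other responders. Response and remission are taken as equal in steroid users and non-users.

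- Share off steroids: D = (1 − p) + p[m·t₁ + (r − m)·t₂]
- Joint rate: J = m[(1 − p) + p·t₁]
- Figure as worded: J/D

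Inputs from the documents: Section 1.2.2.2 reports for Phase 2 that "Clinical response was seen in 68.5% and 93.8% of subjects (observed cases) at Week 12 and Week 52, respectively", with remission of 46.3% and 65.6%. Both remission values are printed against Week 52; pairing them with Weeks 12 and 52 is an assumption. These rates may be too high here, because Section 4.2 admits "Subjects who are not in clinical response and/or clinical remission after completing 12 weeks in the Induction Studies RPC01-3201 or RPC01-3202" and subjects who relapsed in maintenance. A lower pair of 40%/20% is therefore assumed as well. The ranges p = 0.2 to 0.5 and t₁ = t₂ = t = 0.5 to 1 are also assumptions.

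| Rates and dropout | Smallest gap (p = 0.2, t = 1) | Largest gap (p = 0.5, t = 0.5) |
|---|---|---|
| Phase 2 pairs, no dropout | 66.4 − 65.6 = 0.8 | 67.0 − 49.2 = 17.8 |
| 40%/20%, no dropout | 22.7 − 20.0 = 2.7 | 25.0 − 15.0 = 10.0 |
| Phase 2, 20% dropout, all leavers kept as non-responders | 53.0 − 52.5 = 0.5 | 50.0 − 39.4 = 10.6 |
| Phase 2, 20% dropout, only leavers off steroids at entry kept | 55.2 − 52.5 = 2.8 (unrounded) | 57.2 − 39.4 = 17.9 (unrounded) |

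With dropout d, the joint rate is (1 − d)J. The figure as worded is (1 − d)J/[(1 − d)D + d] in the third row and (1 − d)J/[(1 − d)D + d(1 − p)] in the fourth. In the Phase 2 rows both extremes come from the 93.8%/65.6% pair. For example, the 17.8 uses D = 0.5 + 0.5 × 0.938 × 0.5 = 0.7345 and J = 0.656 × 0.75 = 0.492.

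**3. Direction over time.** Take r = 0.685, m = 0.463, p = 0.5 and no dropout.

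| Case | D | J | As worded |
|---|---|---|---|
| Start: all responders complete taper | 84.3% | 46.3% | 55.0% |
| (a) 80% of remitters, 20% of other responders complete | 70.7% | 41.7% | 58.9% (rises) |
| (b) 70% and 48.7% | 71.6% | 39.4% | 55.0% (flat) |
| (c) 50% in both | 67.1% | 34.7% | 51.7% (falls) |
| (d) all complete, but half of tapered remitters flare and stay off | 84.3% | 34.7% | 41.2% (falls) |

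In (a) and (b) fewer subjects are off steroids and the joint rate falls, but the endpoint does not.

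**4. Non-responder imputation does not cure it.** Suppose 100 subjects, 30 with missing data, 50 observed off steroids and 30 of those in remission. The figure as worded is 30/50 = 60.0% if the missing are left out of the denominator and 30/80 = 37.5% if they are kept in. The joint rate is 30/100 = 30.0%.

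**The case against.** The strongest reply is that a joint reading was probably meant. Section 9.2 assigns efficacy analyses to all treated subjects, and a non-responder rule for all proportions fits a fixed denominator. Section 1.2.2.1 names corticosteroid-free remission among the endpoints of the sponsor's ulcerative colitis trial, so this wording may be shorthand for the same idea. The operational definition may also sit in SAP text that was not available. All of this is possible, but the wording still states a restricted denominator where neighbouring items use 'and', and nothing visible makes a subject on steroids a non-responder. If 'off' meant off at entry, the denominator would be a baseline subgroup and the bound against the joint rate would not apply; the documents do not settle that either.

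Two numerical objections stand in part. First, with the same taper completion in remitters and other responders, the figure as worded falls as fewer subjects complete taper, though barely when response is high (67.7% to 67.0% for the 93.8%/65.6% pair at p = 0.5). A rise needs remitters to complete taper more often: at p = 0.5 and 80% in remitters, completion in other responders must be below about 66%. The documents give no such difference, so flat or rising is a possibility, not a prediction. Second, 20% to 50% on steroids has no source. At 5% to 10%, the gap is 0.2 to 3.5 points with the Phase 2 pairs and 0.6 to 1.7 with 40%/20%.

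The consequence is also limited. Nothing is tested, CDAI < 150 regardless of steroid use is reported at the same visits, and all efficacy data are listed.

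**Conclusion.** The concern holds, at minor severity. On its plain wording, with 'off' taken as off at the visit, the endpoint is a conditional proportion whose denominator depends partly on response. It cannot be below the steroid-free remission rate over all treated subjects, and it can mask a fall in that rate. That much follows from the wording and the taper rule. The size does not: it ranges from a fraction of a point to about 18 points over the assumed steroid-use, taper and dropout rates, and is smallest when few subjects enter on steroids. No error rate, power or sample size is affected; what is at risk is the interpretation of one annual descriptive figure.

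**What to change.** Reword the endpoint in Section 2.2.1 and the Protocol Summary as the proportion of all ITT subjects with CDAI < 150 **and** not taking corticosteroids at the visit, stating any minimum steroid-free period. Count subjects on steroids, with missing CDAI, or with missing steroid status as non-responders. Report the number off steroids at each annual visit. If the conditional proportion is kept, label it as remission among subjects off steroids and show its denominator. The same joint numerator among subjects on steroids at entry would be a useful optional addition.

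The cost is one sentence in two places, plus matching SAP text if the SAP does not already say this. Sections 8 and 8.1 already require dated recording of concomitant medication and of medication continuing from the prior study, so no new data are needed. The taper rule is untouched. The one drawback for the sponsor is a less favourable figure.

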3 OVERALL STUDY DESIGN

3.1 Study Design

This is a Phase 3, open-label, multicenter extension study to evaluate safety and explore the long-term efficacy of ozanimod 0.92 mg in subjects with moderately to severely active CD. It is anticipated that approximately [REDACTED] subjects who have participated in a prior study of ozanimod for CD will be eligible to participate in this study if they meet the eligibility criteria and have not met the discontinuation criteria as outlined in the prior studies (eg, RPC01-3201, RPC01-3202, RPC01-3203, and RPC01-2201).

Subjects entering the study from RPC01-2201 will continue to receive ozanimod 0.92 mg/day (equivalent to ozanimod HCl 1 mg). Subjects entering the study from RPC01-3201, RPC01-3202, or RPC01-3203 will initiate ozanimod treatment in accordance with a 7-day dose escalation regimen as follows:

- Days 1 through 4: Ozanimod 0.23 mg daily (equivalent to ozanimod HCl 0.25 mg)
- Days 5 through 7: Ozanimod 0.46 mg daily (equivalent to ozanimod HCl 0.5 mg) (administered as two 0.23-mg capsules)
- Day 8 through End of Study: Ozanimod 0.92 mg daily (equivalent to ozanimod HCl 1 mg)

Subjects who discontinue from treatment due to lack of response, AEs, or other reasons, even if alternative treatment is given, will be followed for [REDACTED] for collection of safety data, including lymphocyte recovery, and for assessment of their disease status. Refer to [REDACTED] and [Section 11.1](#) for further details on lymphocyte recovery monitoring.

The study will be conducted in compliance with the International Council on Harmonisation (ICH) of Technical Requirements for Registration of Pharmaceuticals for Human Use/GCP and applicable regulatory requirements.

3.2 Study Duration for Subjects

This study is expected to continue for a subject for approximately 264 weeks (5 years) plus the Safety Follow-up Visits. Subjects who do not meet discontinuation criteria or withdraw from the study may continue until they complete 264 weeks (5 years) on study treatment, or until the study is discontinued, whichever comes first. Where applicable, the sponsor will provide IP after study

discontinuation as per local or national requirements. The study may be discontinued early if the Sponsor determines that the primary study objectives of demonstration of long-term safety and efficacy have been met, a significant safety and/or efficacy concern is identified, or the sponsor discontinues the development program.

